5.2.1 Investigational agent

[¹⁸F]FLT will be provided by IBA or Cardinal Health pharmacies.

5.2.1.1 Investigational agent administration:

The [¹⁸F]FLT will be brought by shielded carrier to the PET/CT scanner and will be injected intravenously over a 10-15 seconds period using an intravenous catheter under the supervision of an authorized user of radiopharmaceuticals.

Qualified staff or clinical research nurse will be in attendance during the infusion. In the event of an emergency such as an allergic response immediate treatment will be initiated using emergency medication kits available in the Nuclear Medicine/PET Departments. If the participant requires admission due to the severity of the reaction, the participant will be admitted to the Lymphoma service for observation for the NCI site and the appropriate standard operating procedures should be followed for the participating site.

5.2.2 FLT PET/CT Imaging protocol

Immediately following the IV infusion of [¹⁸F]FLT, a dynamic 2D PET emission imaging with the target lesion in the field of view (FOV) will be performed for 60 minutes, immediately followed by a whole body static image. An additional 2D PET emission imaging acquisition will be performed 120 minutes (+/- 10 minutes) post infusion. A corresponding transmission CT will be acquired immediately before each emission scan.

5 ml of venous blood will be obtained ~1 hour and ~2 hours post injection to correct the measured F-18 counts for the % metabolized F-18 FLT. The simplified TLC (thin layer chromatography) method described by Shields et. al.(82) will be performed to determine fraction of parent F-18 FLT remaining in the venous blood at those times.

5.2.3 FDG PET/CT Imaging protocol

Standard image acquisition will be performed approximately 1 hour post injection of F18 FDG.

5.3 Pathology (residual mass arm only)

In patients with FDG avid residual masses (uptake greater than mediastinal blood pool) who would routinely undergo biopsy or fine needle aspiration (FNA), the pathology results will be collected and compared with the corresponding FLT SUV. The presence of any viable lymphoma cells will be considered positive for residual malignancy. Biopsy is not medically

indicated in many patients undergoing therapy and therefore, determination of active disease will be based on clinical follow-up in those patients.

5.4 Treatment modifications

The expected dose of [^{18}F]FLT is 5 mCi. Due to potential unpredictable delays, the total dose administered may be reduced at the discretion of the PI.

5.5 Imaging Interpretation

[^{18}F]FLT PET/CT

[figure not shown]

Figure 8 Kinetic model for [^{18}F]FLT. k_4 is assumed to be negligible at later time points. k_1 and k_2 are assumed to be equal, k_3 is assumed to be the dominate factor in [^{18}F]FLT accumulation in tumors over time.

Preliminary data suggests that [^{18}F]FLT is essentially irreversibly phosphorylated and trapped inside cells (similar to [^{18}F]FDG) during the imaging period. Prior to this point, however, there is a flux of unphosphorylated [^{18}F]FLT (reversible component). If the rate of phosphorylation (k_3) is low, then the early contribution of perfusion to the measured tumor activity is high. Assuming the phosphorylation rate correlates to the proliferative rate, a high rate of phosphorylation means that the cumulative measured tumor activity should be representative of cellular proliferation. The kinetics of FLT distribution has been evaluated in lung(53), brain(63, 83), colon(69) and other tumor types previously.(38, 54, 55) A comparison between the dynamic influx parameter (Patlak graphical analysis (below) and the standardized uptake values (SUV) at 1 and 2 hours post injection will be made. 5cc venous blood samples will be obtained just prior to the 1 and 2 hour imaging sessions to measure for metabolites and measure blood radioactivity. To improve the accuracy of the SUV measurements, the SUV values measured will be corrected for the fraction of non-metabolized FLT remaining in the blood at the time of image acquisition using thin layer chromatography estimation of metabolized fraction as described by Shield et. al.(82)

5.5.1 Compartmental and Patlak(84-87) Graphical Analysis

A 3-compartment data analysis will be performed to estimate values for the rate constants and [^{18}F] FLT flux parameters base on the model in [Figure 4](#) and [Figure 5](#).

The Patlak graphical method enables estimation of the influx rate constant (K_i) and the volume of distribution (V_d) of unphosphorylated [^{18}F] FLT within the ROI from the data. The plot of ROI activity/Plasma Activity vs. $\int (PlasmaActivity * dt) / PlasmaActivity$ will become linear for irreversible systems. The slope of the linear portion is K_i and the y-intercept is V_d . The primary assumptions of these estimations are that the uptake of tracer is irreversible and that exchange of [^{18}F] FLT between the plasma and extracellular compartments has reached equilibrium. The rate of clearance of [^{18}F] FLT from the blood is equal to the Patlak influx rate constant (K_i) and is equal to $k_1k_3/(k_2+k_3)$.

A plasma activity function (the *input function*) is classically obtained from the arterial blood samples. Alternative methods of non-invasively deriving the plasma input function include ROIs drawn over the left atrial cavity (LA)/ basal portion of the left ventricular cavity (LV) or from a normalized population-based input function. Because obtaining an arterial or venous input function would likely adversely effect patient enrollment, for this study an LV image derived input function will be used. (87-90)

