5.5.2 General image parameter extraction

- FLT and FDG uptake greater than surrounding background will be considered positive.
- The “target” will be identified, as a lesion $\geq 1\text{cm}$ with the highest SUV (amongst all identified hypermetabolic lesions).
- All regions/volumes of interest will be saved as DICOM-RT structure sets. Region volumes, and SUV values will be output to an Excel spreadsheet using MIMVista imaging software (www.mimvista.com)
- For the hypermetabolic lesions, an estimated smoothed maximum SUV (SUV_{max}) will be reported as the mean SUV value of an automated 85% maximum pixel value threshold based volume of interest (i.e. the average SUV of the “hottest” 15% of pixels in the user defined lesion). This method reduces the chances of the SUV_{max} value being dominated one or more “noisy” pixel values.
- All lesions will be followed from baseline with the same lesion number, even if they have resolved.
- For quality control, mediastinal and left ventricular blood pool (BP) SUV means, spleen, and liver SUV mean will be measured in all FLT and FDG scans.
 - To measure the left ventricular cavity BP SUV_{mean} , the mean SUV of a 1 cm spherical volume of interest (VOI) will be placed in the left ventricular cavity, avoiding the myocardial wall
 - For liver and spleen SUV_{mean} , a spherical VOI of 2 to 5 cm in diameter will be placed in a homogeneous area in the center of the organ (excluding the central hilum of the liver), and the mean SUV recorded.
- For the FLT images, the K_i Patlak influx parameter will be extracted from the 60 minute dynamic data. SUV values (corrected for the fraction of unmetabolized FLT (as

determined by thin layer chromatography (TLC)) will be recorded for the 1- and 2- hour static images.

- For the primary analyses, the 1- hour SUV (SUV₁) parameters will be used
- For the FDG images SUV values will be recorded for the 1 hour static images.
- On transmission CT, lesion dimensions will be determined in perpendicular planes where the lesion appears largest.

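### Tumour Ki is fitted to a left-ventricular image curve of total F-18 with no stated parent-FLT correction, so the plan as written gives a Ki that is biased low

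*Combined protocol and SAP*

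**What the plan says.** Section 5.5.1 obtains Ki as the slope of a Patlak plot of region activity over plasma activity, and equates it with k1k3/(k2+k3) for FLT. A sampled input is ruled out: "Because obtaining an arterial or venous input function would likely adversely effect patient enrollment". Instead, "for this study an LV image derived input function will be used". No step in 5.5.1 removes metabolites from that curve.

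Section 5.2.2 draws venous blood at about 1 and 2 hours "to correct the measured F-18 counts for the % metabolized F-18 FLT", with TLC used "to determine fraction of parent F-18 FLT remaining in the venous blood at those times". Section 5.5 then ties the correction to the SUV values. Section 5.5.2 lists the two measures side by side: "the K_i Patlak influx parameter will be extracted from the 60 minute dynamic data", and the sentence after it attaches the TLC correction to the 1-hour and 2-hour SUVs.

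Ki appears in secondary objective 2c (tumour, selected normal organs and mediastinal blood pool) and in Tables 3 and 4. Section 5.5.2 assigns the primary analyses to the 1-hour SUV.

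**The concern.** The identity Ki = k1k3/(k2+k3) holds for FLT only if the input is parent FLT. An LV image curve cannot tell parent tracer from labelled metabolite, so both the denominator and the running integral of the Patlak plot are too large once metabolites are present.

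The plan treats metabolism as important enough to draw blood and correct the SUVs. Objective 2c would then set TLC-corrected SUVs beside a Ki that has had no such correction. Because the bias depends on k3 as well as on the parent fraction, no single rescaling factor can remove it afterwards. Reported Ki values, and any description of Ki beside SUV, would partly reflect tracer metabolism.

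**Working it through.** The documents give no figure for Ki, the parent fraction or the bias, so there is no stated result to reproduce. The check has three parts.

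**1. Direction.** Let C(t) be parent FLT in plasma, f(t) the parent fraction (1 at injection, falling), and G = C/f the total F-18 curve. Write P for the integral of C and T for the integral of G, both from injection. Under the plan's own assumptions (irreversible uptake, equilibrium reached), region activity is R = Ki·P + V·C, where V is the distribution volume.

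- Parent input: R/C = Ki·(P/C) + V, a line with slope Ki.
- Total input: y = R/G = Ki·(P/G) + V·f, and x = T/G.
- Differentiating, with h = −G′/G², the local slope is [Ki·(f + P·h) + V·f′] / (1 + T·h).

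While total blood activity is falling, h is at least 0. Also f < 1, P < T and f′ ≤ 0. The slope is therefore below Ki.

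**2. Why the size depends on k3.** The V·f′ term lowers the slope further, in proportion to V/Ki. In this model V = k1k2/(k2+k3)², so V/Ki = k2/[k3(k2+k3)]. The plan states that "k_1 and k_2 are assumed to be equal"; taking both as 0.1/min (assumed):

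- k3 = 0.02/min: Ki = 0.1×0.02/0.12 = 0.0167/min; V/Ki = 0.1/(0.02×0.12) = 41.7 min.
- k3 = 0.10/min: Ki = 0.1×0.10/0.20 = 0.05/min; V/Ki = 0.1/(0.10×0.20) = 5 min.

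Slow phosphorylation therefore suffers the larger bias.

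**3. Size.** The irreversible model was simulated for 60 minutes and the Patlak slope fitted over 20–60 minutes, once with parent and once with total input. Assumed, and not in the documents: the blood-curve shape, the rate constants, the fit window, and the parent fraction at 60 minutes (PF). Set A uses k1 = k2 = 0.1/min, k3 = 0.02–0.10/min, and exponential or linear decline of f. Set B adds a 5% blood volume, lets k1 = k2 be 0.1 or 0.2/min, and uses exponential or saturating decline.

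| PF at 60 min | Set A: reduction in Ki | Set B: reduction in Ki |
|---|---|---|
| 0.95 | – | 2–5% |
| 0.90 | 5–10% | 5–10% |
| 0.80 | 10–19% | 11–21% |
| 0.70 | 15–29% | 18–34% |
| 0.60 | 20–39% | 26–51% |

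The set A reductions are 1 minus slope ratios of 0.90–0.95, 0.81–0.90, 0.71–0.85 and 0.61–0.80. A repeat with two other multi-exponential blood curves gave ratios of 0.95–0.98 at PF 0.95 and 0.60–0.81 at PF 0.6, in line with set A. The total-input slope was the lower one in every scenario, including those in which metabolites entered the extracellular space.

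**4. Blood pool.** A blood-pool region contains G itself. With total input, y = G/G = 1 and the slope is zero. With parent input, y = G/C = 1/f, which rises as f falls and so yields a positive slope with no influx. In one set of runs this was about 0.0008/min at PF 0.9 and 0.0034/min at PF 0.6; another blood curve reached 0.0051/min at PF 0.6. Any correction has to allow for this.

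**The case against.** The strongest reply is that the correction is unstated, not refused. The wording of 5.2.2 about measured F-18 counts could extend to LV counts, 5.5 says the samples also measure blood radioactivity, and 5.5.1 speaks of a plasma activity function. A reader might infer that the plan decides against correcting Ki; the documents do not show that. What remains is that no section names the input curve as corrected. A curve correction also needs a shape before 1 hour, and none is given. Two analysts could follow the text and get different Ki values. The works cited for the LV input cannot be assumed to settle this: by title, three of the four concern FDG or glucose utilization.

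The second reply is that no planned test is shown to change. This largely stands. Section 3.4 quotes tumour SUVs of 4–7, whereas the assumed rate constants give a Ki of about 0.017–0.05/min. If 2c pairs Ki with SUV, a bias of this size cannot alter the sign of a difference. If it compares tissues within one scan, they share one input, and with k1 and k2 fixed the ordering was preserved. The damage is to the Ki estimates themselves.

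Third, corrected Ki is not exact. With metabolites in extracellular space, one run (PF 0.6, k3 0.02/min) put parent-input Ki at 1.13 times the truth. Parent input was still closer to the truth in nearly all cases examined.

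**Conclusion.** The point holds as a gap in the specification of a secondary measure. Carried out as written, tumour Ki is biased low. The direction follows from the plan's own model whenever the parent fraction falls below 1 and total blood activity is declining. The size rests wholly on assumed parent fractions, blood curves and rate constants: a few percent if the fraction stays near 0.95, about 40% at 0.6 in simple models, and up to 51% in one set of runs.

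Three stronger readings are tempting and are not supported:

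- That the primary results are affected. They use the 1-hour SUV.
- That apparent changes in Ki between scans would mislead a planned analysis. Ki is recorded at each visit, but percent change is defined only for SUV (5.5.3, objective 2d).
- That the liver-test limits in 4.1.3, or treatment itself, make the parent fraction vary. No section links either to FLT metabolism, and the point does not need it.

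It is worth correcting because the blood is already being drawn, but it does not threaten the trial's main conclusions.

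**What to change.** Add to 5.5.1:

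- For tumour and normal-organ Ki, in both the Patlak and the compartmental fits, multiply the LV curve by a prespecified monotone parent-fraction function equal to 1.0 at injection and anchored to the TLC value at about 1 hour.
- Keep the uncorrected total-activity LV curve for any blood-volume term.
- Do not interpret a parent-input Patlak slope for mediastinal blood pool as influx; it is an artefact of the correction. This matters because 2c names that region.
- Report uncorrected Ki as a sensitivity analysis.

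The cost is a few sentences and one extra computing step. The blood samples and TLC are already in the protocol, so there is no added patient burden. Where dynamic images and TLC values were kept, patients already scanned can be reanalysed. The downsides are that the parent fraction before 1 hour is interpolated, and that corrected Ki can still be somewhat biased if metabolites enter tissue.

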5.5.2 General image parameter extraction

- FLT and FDG uptake greater than surrounding background will be considered positive.
- The “target” will be identified, as a lesion $\geq 1\text{cm}$ with the highest SUV (amongst all identified hypermetabolic lesions).
- All regions/volumes of interest will be saved as DICOM-RT structure sets. Region volumes, and SUV values will be output to an Excel spreadsheet using MIMVista imaging software (www.mimvista.com)
- For the hypermetabolic lesions, an estimated smoothed maximum SUV (SUV_{max}) will be reported as the mean SUV value of an automated 85% maximum pixel value threshold based volume of interest (i.e. the average SUV of the “hottest” 15% of pixels in the user defined lesion). This method reduces the chances of the SUV_{max} value being dominated one or more “noisy” pixel values.
- All lesions will be followed from baseline with the same lesion number, even if they have resolved.
- For quality control, mediastinal and left ventricular blood pool (BP) SUV means, spleen, and liver SUV mean will be measured in all FLT and FDG scans.
 - To measure the left ventricular cavity BP SUV_{mean} , the mean SUV of a 1 cm spherical volume of interest (VOI) will be placed in the left ventricular cavity, avoiding the myocardial wall
 - For liver and spleen SUV_{mean} , a spherical VOI of 2 to 5 cm in diameter will be placed in a homogeneous area in the center of the organ (excluding the central hilum of the liver), and the mean SUV recorded.
- For the FLT images, the K_i Patlak influx parameter will be extracted from the 60 minute dynamic data. SUV values (corrected for the fraction of unmetabolized FLT (as

determined by thin layer chromatography (TLC)) will be recorded for the 1- and 2- hour static images.

- For the primary analyses, the 1- hour SUV (SUV₁) parameters will be used
- For the FDG images SUV values will be recorded for the 1 hour static images.
- On transmission CT, lesion dimensions will be determined in perpendicular planes where the lesion appears largest.

5.5.3 Early response arm

- The percent of decrease or increase in SUV uptake in post cycle 2 and end of treatment scans in comparison with baseline scans will be calculated as follow:

$$\frac{\text{SUV}_{\text{max}} \text{ post cycle 2 or end of treatment} - \text{baseline SUV}_{\text{max}}}{\text{Baseline SUV}_{\text{max}}}$$

Table 3 Image Analysis Parameters for Early Response Arm

Pre-treatment	Mid-treatment	Post Treatment
FLT (K _i , SUV ₁ , SUV ₂)	FLT (K _i , SUV ₁ , SUV ₂)	FLT (K _i , SUV ₁ , SUV ₂)
FDG (SUV ₁)	FDG (SUV ₁)	FDG (SUV ₁)
CT (bidirectional measurements)	CT (bidirectional measurements)	CT (bidirectional measurements)

5.5.4 Residual mass arm

- The size of the residual mass will be determined on CT and will include the entire length of the mass visible on CT (i.e. if only a portion of the mass is hypermetabolic, the anatomical size will be determined by the entire mass length, not just the portion which appears hypermetabolic)
- The length used for the inclusion criteria is the longest measureable length

Table 4 Image Analysis Parameters for the Residual Mass arm

FLT (K _i , SUV ₁ , SUV ₂)
FDG (SUV ₁)
CT (bidirectional measurements)

6 Protocol evaluations

6.1 Study Calendar

Table 5

	Pre-study	Pre-therapy (biopsy for the Residual Mass arm)	Post 2-cycles	End of study
Enroll in CALGB 50303 or other lymphoma therapy trial or undergoing a new course of treatment of lymphoma at another	X			

	Pre-study	Pre-therapy (biopsy for the Residual Mass arm)	Post 2-cycles	End of study
facility				
Informed Consent	X			
Check Liver Function	X	X	X	X
Urine or Serum HCG	X	X	X	X
Early Response Arm				
FDG PET/CT	X	X ^c	X	X
FLT PET/CT		X ^c	X	X ^a
Residual Mass Arm				
FDG PET/CT	X ^b			
FLT PET/CT		X		

^aThe FLT PET/CT scan will be performed at least 12 hours after, and +/- 2 weeks of, the FDG PET/CT study

^bIf not performed at NIH or WRNMMC a repeat FDG PET/CT will be performed according to the prescribed FGD PET/CT protocol within 2 weeks of the FLT PET/CT study

^c Baseline FDG and FLT PETs must be performed prior to initiation of the current/new therapy in patients in the Early Response arm

6.2 Concurrent Therapies

No restrictions

6.3 Surgical Guidelines

FDG PET imaging must be performed >2 week following any surgical procedure to the target lesion.

6.4 Radiation Therapy Guidelines

In patients in whom the target lesion received radiation therapy, the FDG PET imaging must be performed >8 weeks following the completion of radiation therapy.

6.5 Supportive care guidelines

In the event that a patient has a reaction (allergic) to the contrast agent or radiotracer, all appropriate medical measures will be taken immediately. In rare instances, this may entail admission to the hospital on the Medical Oncology (Inpatient Lymphoma) service for observation and the appropriate standard operating procedures should be followed for the participating site.

6.6 Off Study Criteria

Subjects will be enrolled in the study beginning with their consent for [¹⁸F]FLT imaging and ending following completion of all FLT PET/CT imaging. Correlative clinical response data will also be obtained from data collected from the lymphoma therapy trial.

Once a subject is taken off study, no further data can be collected, with the exception of follow-up clinical data from the patients referring physicians. Patients will be taken off the study if:

- Patient experiences an adverse event that prohibits them from completing the [¹⁸F]FLT imaging sessions
- Patients voluntarily withdraw from the study

- Patient completes all FLT PET/CT imaging
- Death

6.6.1 Directions for NCI

Authorized staff must notify Central Registration Office (CRO) when a subject is taken off-study. An off-study form from the web site (<http://intranet.cancer.gov/ccr/welcome.htm>) main page must be completed and faxed to [contact].

6.6.2 Directions for participating site

All subjects must be registered through the NCI Central Registration Office (CRO). The CRO is open from 8:30am to 5:30pm EST Monday through Friday, excluding federal holidays. An off-study form will be supplied by the Coordinating Center, NCI CCR. Send the completed off-study form to the Coordinating Center's Research Nurse; insert name, telephone number, and email.

7 Data collection and evaluation

7.1 Data collection

Demographic and summary data will be collected by research nurse or designee and entered in a password protected file in NCI C3D. The data will be entered at least on a weekly basis. Participating institutions will be trained in the use of NCI C3D and database access will be provided to site staff based on their designated duties.

The following is a list of specific data elements that **will** be collected or recorded in the database:

- demographics,
- histological type and disease stage,
- diagnosis date
- history of previous therapy (including dates of therapy)
- Date Informed Consent signed
- ECOG Status
- Labs
- Radiotracer dose amount & time.
- The following adverse events of any grade:
 - Localized discomfort at the IV injection site
 - Pain
 - Respiratory difficulties
 - Flushing
 - Dizziness
 - Itching/rash
 - Any other symptoms that could be secondary to an anaphylactic reaction
 - Any sign of illness or symptoms that appear or worsen after the F-18 FLT infusion

Imaging data will include storage of the images from each time point and intensity measurements from the tumor will be stored on a secure, password protected lab imaging database. [name] will serve as the study monitor responsible for the protocol.

The images will be stored on a secure database completely anonymized and administered by the Cancer Imaging Program, NCI. Access to these systems is restricted to authorized users.

Please note that follow-up clinical data may be collected from the patients referring physicians.

7.2 Response Criteria:

7.2.1 Early Treatment Arm

Overall response will be assessed according to the Cheson revised response criteria, 2007.(91). This data will be collected under the therapy trial in which the patient is also enrolled. For primary analyses, CR and CRu will be considered positive for response.

Table 6 Summary of the response criteria

Response	Definition	Nodal Masses	Spleen, Liver	Bone Marrow
CR	Disappearance of all evidence of disease	(a) FDG-avid or PET positive prior to therapy; mass of any size permitted if PET negative (b) Variably FDG-avid or PET negative; regression to normal size on CT	Not palpable, nodules disappeared	Infiltrate cleared on repeat biopsy; if indeterminate by morphology, immunohistochemistry should be negative
PR	Regression of measurable disease and no new sites	≥ 50% decrease in SPD of up to 6 largest dominant masses; no increase in size of other nodes (a) FDG-avid or PET positive prior to therapy; one or more PET positive at previously involved site (b) Variably FDG-avid or PET negative; regression on CT	≥ 50% decrease in SPD of nodules (for single nodule in greatest transverse diameter); no increase in size of liver or spleen	Irrelevant if positive prior to therapy; cell type should be specified
SD	Failure to attain CR/PR or PD	(a) FDG-avid or PET positive prior to therapy; PET positive at prior sites of disease and no new sites on CT or PET (b) Variably FDG-avid or PET negative; no change in size of previous lesions on CT		
Relapsed disease or PD	Any new lesion or increase by ≥ 50% of previously involved sites from nadir	Appearance of a new lesion(s) > 1.5 cm in any axis, ≥ 50% increase in SPD of more than one node, or ≥ 50% increase in longest diameter of a previously identified node > 1 cm in short axis Lesions PET positive if FDG-avid lymphoma or PET positive prior to therapy	> 50% increase from nadir in the SPD of any previous lesions	New or recurrent involvement

Abbreviations: CR, complete remission; FDG, [¹⁸F]fluorodeoxyglucose; PET, positron emission tomography; CT, computed tomography; PR, partial remission; SPD, sum of the product of the diameters; SD, stable disease; PD, progressive disease.

